1.0 Data Analyses

1.1 Study Population

The study population will include up to 20 adults (18 years of age or older) who are audiological and medical candidates to receive a Nucleus® cochlear implant and are capable of completing the study evaluation.

1.2 Sample Size

Based on the variability observed in the FAST take-home trial in experienced ACE recipients, it was determined using G*Power (Faul et al. 2007) that a minimum of 11 subjects would provide at least 90% power for hypothesis testing of the two co-primary endpoints at the 0.025 alpha level. More subjects will provide additional power or a similar degree of power for more conservative assumptions. Because the non-inferiority sample size calculation assumes a true difference of 0 between ACE and FAST, we propose a sample size of 20 subjects to allow for:

1. the possibility that variability will be greater than expected,
2. the possibility of a clinically insignificant difference between the two strategies,
3. the possibility of subject attrition.

The planned sample size of 20 subjects will provide adequate power for the primary efficacy endpoints. The following general assumptions have been made:

- Non-inferiority tests with M_2 margins of 10 rationalized arcsine units (rau, Studebaker 1985) for CNC word recognition and -2 dB for average BKB sentence recognition across two types of noise (babble and speech-shaped noise)
- One-sided 0.025 alpha levels
- Assumed distribution for population (standard deviation) based on the FAST take-home trial in experienced ACE recipients
- Desire for 90% power

The power analyses for the primary test metrics are provided below.

Sample size calculation for CNC word recognition:

Scenario (Non-inferiority)	Minimum Evaluable Sample Size Required
One-sided 0.025 alpha, 90% power, SD = 7.20 rau, $M_2 = 10$ rau, true difference = 0	8

Sample size calculation for BKB sentence reception (using previous data from testing in babble only):

Scenario (Non-inferiority)	Minimum Evaluable Sample Size Required
One-sided 0.025 alpha, 90% power, SD = 1.84, $M_2 = -2$ dB, true difference = 0	11

1.3 Safety

1.3.1 Primary Safety Objective

An adverse event (AE) is any undesirable clinical or medical occurrence associated with the use of the device, procedure, or participation in the study, which does not result in serious injury or illness related to the surgical procedure or the device.

Adverse events that occur during this study may be associated with the implant procedure, including those from general anesthesia, or specifically associated with the use of the device. An adverse event will be considered to be device-related when, in the judgment of the Primary Investigator, there is a logical connection between the use of the device and the occurrence of the event, above and beyond the study procedure itself. Adverse events associated with cochlear implantation in previous investigations include tinnitus, dizziness, swelling, facial nerve stimulation, and open and/or short circuit electrodes, among others.

Adverse events will be counted regardless of severity, seriousness, onset, duration, or relation to study treatment.

A serious adverse event (SAE) is any untoward medical occurrence that

- results in death
- is life-threatening
- requires inpatient hospitalization or prolongation of existing hospitalization
- results in persistent or significant disability/incapacity
- requires medical or surgical intervention to prevent life-threatening illness or injury or permanent impairment to a body structure or a body function
- leads to fetal distress, death, or congenital abnormality or birth defect
- is a medically important event or reaction

For any SAE, if the Primary Investigator judges that there is a logical connection (caused or contributed to) between the use of the device and the occurrence, the SAE will be noted as device-related.

1.3.1.1 *Analysis of Primary Safety Objective*

All Adverse Events will be tabulated according to the study interval, the number of procedure-related events, and the number of device-related events. Procedure- and device-related Adverse Events will be summarized as rates, where the numerator for each rate will be the number of subjects with at least one procedure- or device-related event, and the denominator will be the total number of subjects. No formal statistical comparisons will be conducted.

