5.0 Investigational Procedures

5.1 Design Overview

This study will implement a within-subject crossover design with 20 subjects. All subjects will receive each of the treatments – the ACE and FAST strategies. In this repeated measures design, half of the subjects, Group 1, will be mapped with FAST first and the other subjects, Group 2, with ACE first, using formalized mapping procedures. Endpoint speech perception testing, additional to standard clinical testing, will be conducted after 3 months of use with the initial strategy. At the 3-month post initial activation (IA) session, each recipient will be programmed with the crossover strategy. The crossover strategy will then be assessed after 3 months of take-home use at 6 months post IA (refer to Table 1). As indicated in Table 1, fine-tuning of the cochlear implant stimulation levels (i.e. MAP) will occur at 1 week and 1 month after receiving each strategy. Standard clinical testing will also occur at 3 months and 6 months post activation.

The order in which the subjects are programmed with the ACE and FAST strategies will be counterbalanced according to group; Group 1 will start with FAST and Group 2 with ACE. Subjects will be randomly assigned to either Group 1 or 2. Standardized programming procedures will be used to program the FAST and ACE strategies. Subjects will be blinded as to the identity of the strategies.

The study design strikes a balance between providing a reasonable amount of take-home experience with each of the strategies and obtaining outcome comparison data for the strategies within the required timeframe. It is acknowledged that maturational effects are not eliminated with crossover to the alternative strategy at 3 months post IA. The exclusion criteria for enrollment will provide control over some of these variables. To further address maturational effects, subjects' scores from the Reading Span Test (a cognitive test of working

CONFIDENTIAL

memory) will be included as a statistical covariate to understand differences in adaptation that might be associated with working memory.

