6.2 Unanticipated Adverse Device Effects

Unanticipated adverse device effects refer to any event not identified above that represents a “serious adverse effect on health or safety or any life-threatening problem or death caused by, or associated with, a device if that effect, problem or death was not previously identified in nature, severity, or degree of incidence in the investigational plan or application, or any other unanticipated serious problem associated with a device that relates to the rights, safety, or welfare of subjects.” [FDA 21 CFR 812.3(s)]

Investigators are to inform their respective Institutional Review Boards (IRBs) and Cochlear Americas immediately if an unanticipated adverse device effect is suspected (no more than 10 working days after the investigator learns of the effect). If the case is determined to be an unanticipated adverse device effect, the investigator will fill out an “Unanticipated Adverse Device Effect Form.” Cochlear Americas will report the results of an evaluation of the unanticipated adverse device effect to the FDA and all other reviewing IRBs and investigators within 10 working days after first receiving notice of the event.

CONFIDENTIAL

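### The plan contradicts itself on whether serious procedure- or device-related events count in the primary safety rates

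*Combined protocol and SAP*

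**What the plan says.** SAP 1.3.1 defines an AE as an undesirable occurrence associated with the device, the procedure or study participation, and then restricts it to one "which does not result in serious injury or illness related to the surgical procedure or the device". Protocol 6.0 repeats the restriction word for word. Both documents define SAEs separately, by the usual outcome list, and neither says that SAEs are a subset of AEs.

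The same SAP section then gives a counting rule: "Adverse events will be counted regardless of severity, seriousness, onset, duration, or relation to study treatment". For SAEs it adds that, if the investigator judges that use of the device caused or contributed to the event, "the SAE will be noted as device-related". There is no matching sentence for SAEs related to the procedure.

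The analysis is in SAP 1.3.1.1. All AEs are tabulated, and "Procedure- and device-related Adverse Events will be summarized as rates". For these, "the numerator for each rate will be the number of subjects with at least one procedure- or device-related event". The divisor is every subject in the study. No SAE table or SAE rate is named, and no formal comparison is planned.

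Protocol 6.1 requires the Adverse Event form for any AE and for every adverse device effect. It defines the latter by association with device use or study participation, without a limit on seriousness. Protocol 6.2 covers serious device effects that are unanticipated, including any effect that "was not previously identified in nature, severity, or degree of incidence in the investigational plan or application".

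**The concern.** The related-event rates are the whole of the planned analysis for the objective that the SAP calls primary for safety. If an analyst applies the written definition, an event that causes serious harm through surgery or the device is not an AE. It therefore enters neither the AE tabulation nor either rate, and no SAE summary would recover it. If the analyst applies the counting rule, the same event is counted. Two competent people following the same SAP could report different safety results from the same data, and sites could classify the same event differently. A reader of the report could not tell which rule had been used.

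**Working it through.** The documents state no figure to reproduce, so the check sets the texts side by side and then gives the scale.

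**1. Text that leaves serious related events out.**
- The AE definition (SAP 1.3.1, protocol 6.0) removes events causing serious harm related to surgery or device.
- The rates in SAP 1.3.1.1 are rates of procedure- and device-related AEs, which is the narrowed term.
- No SAE table or rate is planned.

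**2. Text that brings them in.**
- The counting rule (SAP 1.3.1) says that seriousness is disregarded in counting.
- The SAE relatedness sentence (SAP 1.3.1) classifies SAEs as device-related, and the device-related rate is the only planned summary that could use that classification.
- The numerator (SAP 1.3.1.1) refers to an event, not to a non-serious one.

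**3. Does the second group settle the matter?** No.
- The counting rule governs AEs, a term already narrowed by the definition. It is not empty under the literal definition: a serious event linked only to study participation would remain an AE and be counted, while a serious event related to surgery or device would stay out.
- The word for event in the numerator sits in a clause that explains rates of AEs, so it does not clearly widen them.
- The counting rule appears only in the SAP. Protocol 6.0 to 6.2, which sites use to record events, does not contain it.

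**4. What is recorded under the protocol, taking the AE definition literally.**

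| Serious event | Route to a form |
|---|---|
| Associated with device use, anticipated or not | Adverse Event form, as an adverse device effect (6.1) |
| Associated with study participation | Adverse Event form, as an adverse device effect (6.1) |
| Device effect that is also unanticipated | Additionally the separate unanticipated-effect form (6.2) |
| Purely procedure-related, judged not associated with participation | None stated |

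The last row is possible because protocol 5.4 leaves the surgery unmodified, so a site could regard a surgical or anesthetic event as unconnected with being in the study.

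**5. Scale.** Protocol 5.1 gives the number of subjects: "This study will implement a within-subject crossover design with 20 subjects". The change in a rate from leaving out k subjects whose only event of that type is serious is k/20:
- k = 1: 1/20 = 5 percentage points
- k = 2: 2/20 = 10 percentage points
- k = 3: 3/20 = 15 percentage points

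The range k = 1 to 3 is an assumption. A subject who also has a non-serious related event of the same type is in the numerator under either reading and changes nothing.

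**The case against.** The strongest reply is that the counting rule is the only sentence in SAP 1.3.1 that says how events are counted, that it expressly disregards seriousness, and that the SAE relatedness sentence would serve little purpose if SAEs stayed out of the device-related rate. On this view the intent is inclusion and the definition is loosely worded. This stands as far as it goes: a reader might infer from the definition that the rates simply omit serious related events, and the documents do not support that as a settled outcome. They support two conflicting instructions with no rule of precedence.

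A reader might also infer that the protocol has no recording route for serious related events in general. That goes too far. Protocol 6.1 puts every adverse device effect on the Adverse Event form whatever its seriousness, and does so even when the risk was acknowledged in the consent form. It also states an intention to record procedure-related AEs. Only the narrow class in the last row of the table is left, and only if the AE definition is read literally against that intention.

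It is also fair to say that safety is descriptive here, that study success rests on the two efficacy co-primaries, and that the implants, processor hardware and surgery are unchanged. That limits the consequences but does not remove the contradiction in the primary safety summary.

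**Conclusion.** The point holds as an internal contradiction. The AE definition, read literally, excludes serious procedure- and device-related events from the primary safety rates. The counting rule in the same SAP section points to inclusion, and no SAE summary is planned that would make the choice harmless. The ambiguity is greater for procedure-related events, because the SAE relatedness sentence in the SAP addresses only the device, and the adverse device effect wording in protocol 6.1 addresses only device use and study participation.

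The size is 5 percentage points for each subject whose only related event is serious. This assumes that all 20 planned subjects form the denominator; the step is larger if fewer are enrolled. Since no SAE rate is given, the expected effect cannot be estimated. No hypothesis test, alpha level, power or efficacy conclusion is touched. The wording is wrong as it stands and should be corrected, but it does not threaten the validity of the trial.

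**What to change.** 1. In SAP 1.3.1 and protocol 6.0, delete the clause "which does not result in serious injury or illness related to the surgical procedure or the device", and state that SAEs are a subset of AEs. The counting rule then stands without contradiction.
2. In SAP 1.3.1.1, state that SAEs count in both the procedure-related and the device-related numerators. This needs a procedure-relatedness judgment for SAEs beside the existing device-relatedness one.
3. In protocol 6.1, state that serious procedure-related events are recorded on the Adverse Event form, so that the data needed for item 2 are collected.

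Separate table rows for subjects with any SAE, any procedure-related SAE and any device-related SAE would be good practice but are optional once item 2 is in place.

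The cost is a few sentences in the two documents. Design, sample size and efficacy analysis are unchanged. The only downside is that the reported related-event rates may be slightly higher than under the literal definition.

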1.4 Efficacy

Efficacy of the FAST strategy will be determined by a comparison of outcome measures with subjects using ACE versus FAST. The test metrics for this purpose will include CNC word recognition, BKB sentence reception in babble and in speech-shaped noise, battery life duration, and SSQ ratings.

1.4.1 Primary Efficacy Objectives

The two co-primary efficacy endpoints will be based on analyses of CNC word recognition and BKB sentence reception in babble and speech-shaped noise after 3 months of experience with each strategy (collected at 3-months and 6-months post initial activation). The objective of the two co-primary efficacy endpoints is to test for non-inferiority of FAST compared to ACE. Study success will be defined by rejection of the null hypotheses for both of the two co-primary endpoints.

1.4.1.1 *First Co-Primary Efficacy Endpoint: CNC Word Recognition*

The objective of the first co-primary efficacy analysis is to demonstrate non-inferiority of FAST compared to ACE for word recognition in quiet as evaluated with the CNC test. Success for the first co-primary endpoint will be based on rejection of the null hypothesis of inferiority, with a non-inferiority margin of 10 rau based on clinical judgment and variability observed in previous studies ($M_2 = 10$). The treatment effect will be estimated using a LMM adjusted for period and sequence and a random effect for subject. If the upper 97.5% confidence bound is less than 10 rau, statistical significance will be met at the 0.025 alpha level. The first co-primary endpoint is represented by the following hypotheses:

$$H_0: CNC_{diff} \geq 10 \text{ rau},$$

$$H_a: CNC_{diff} < 10 \text{ rau},$$

where:

CNC_{diff} = ACE – FAST treatment difference, controlling for period and sequence effects, for CNC word recognition in rationalized arcsine units (rau).

1.4.1.2 *Second Co-Primary Efficacy Endpoint: BKB Sentence Reception in Noise*

The objective of the second co-primary efficacy analysis is to demonstrate non-inferiority of FAST compared to ACE for sentence reception in babble and speech-shaped noise as evaluated with the BKB test. The average speech reception threshold (SRT) across the two noise types will be taken for each subject. For the speech reception threshold procedure employed in this study, results are presented as the signal-to-noise ratio (SNR) at which 50% recognition is achieved. Therefore, a lower SRT in dB indicates better performance. Success for the second co-primary endpoint will be based on rejection of the null hypothesis of inferiority, with a non-inferiority margin of -2dB based on clinical judgment and variability observed in previous studies ($M_2 = -2\text{dB}$). The treatment effect will be estimated using a LMM adjusted for period and sequence and a random effect for subject. If the lower 97.5% confidence bound is greater than -2 dB , statistical significance will be met at the 0.025 alpha level. The second co-primary endpoint is represented by the following hypotheses:

$$H_0: SRT_{diff} \leq -2\text{dB},$$

$$H_a: SRT_{diff} > -2\text{dB},$$

where:

SRT_{diff} = ACE – FAST treatment difference, controlling for period and sequence effects, for SRT averaged across two noise types.

1.4.2 Secondary Efficacy Objectives

1.4.2.1 *Battery Life*

The secondary efficacy endpoint for battery life will be based on battery logs as recorded by the subject during the take-home period with each strategy. The objective of this secondary endpoint is to demonstrate superiority of FAST compared to ACE for battery life. Success for this secondary endpoint will be based on rejection of the null hypothesis that battery life with FAST is less than or equal to battery life with ACE. The estimated within-subject mean difference in battery life between FAST and ACE will be reported with a 95% confidence interval. A one-sided t-test will be conducted at the 0.025 significance level. The secondary endpoint for difference in battery life is represented by the following hypotheses:

$$H_0: BLD \leq 0,$$

$$H_a: BLD > 0,$$

where:

BLD = within-subject battery life difference for FAST – ACE.

1.4.2.2 *Speech, Spatial, and Qualities of Hearing Scale (SSQ12-C)*

The secondary efficacy endpoint for the quality and speech understanding questionnaire will be based on subjects' responses on the SSQ12-C as recorded one month after crossover from the first strategy to the second strategy. The SSQ12-C is a comparative, closed-ended questionnaire composed of 12 items assessing speech perception, spatial hearing, sound quality, and listening effort. A response of 0 on the questionnaire indicates equivalent performance between FAST and ACE, while positive or negative responses indicate a preference for one strategy over the other.

The difference between the two study groups will be evaluated with a two-sided t-test using average responses on the SSQ12-C across the 12 questions within each group. Success for this secondary endpoint will be based on a non-significant result, indicating no difference between the two groups in terms of crossing over from one strategy to the other (i.e., not rejecting the null hypothesis that responses from the two groups are equivalent). The mathematical expressions are:

$$H_0: \mu_{G1} = \mu_{G2},$$

$$H_a: \mu_{G1} \neq \mu_{G2},$$

where:

μ_{G1} = mean response value on the SSQ12-C for Group 1;

μ_{G2} = mean response value on the SSQ12-C for Group 2.

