8.0 Data Analysis

8.1 Statistical Analysis

Endpoint speech perception data will be analyzed using linear mixed models (LMM) in order to test for treatment effects while controlling for period and sequence effects. Non-inferiority will be tested with the confidence intervals of the treatment effects from the statistical models. If the one-sided limit of the 97.5% confidence bound does not exceed the non-inferiority margin, statistical

CONFIDENTIAL

significance will be met at the 0.025 alpha level. The non-inferiority margin for word recognition is 10 rationalized arcsine units (rau). The non-inferiority margin for the sentence in noise tests with an adaptive SNR is –2dB. The non-inferiority margins are based on clinical judgment and variability observed in previous studies testing FAST and ACE.

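### The battery-life t-test leaves out period: if battery life shifts between periods, the interval widens and, with unequal groups, the estimate is biased

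*Combined protocol and SAP*

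**What the plan says.** SAP 1.4.2.1 defines the endpoint as a paired quantity: "BLD = within-subject battery life difference for FAST – ACE". The test is stated in one sentence, "A one-sided t-test will be conducted at the 0.025 significance level", and the estimate in another: "The estimated within-subject mean difference in battery life between FAST and ACE will be reported with a 95% confidence interval". Read together, these describe a one-sample t-test on the differences, with neither period nor sequence in it.

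For the co-primary endpoints, SAP 1.4.1.1 says "The treatment effect will be estimated using a LMM adjusted for period and sequence and a random effect for subject", and SAP 1.4.1.2 does the same. Protocol 8.1 applies the mixed model to the speech perception data only. No other section adds a period adjustment for battery life.

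On the design, protocol 5.1 says "This study will implement a within-subject crossover design with 20 subjects". Assignment to sequence is random, and "half of the subjects, Group 1, will be mapped with FAST first"; the rest start with ACE. Protocol 5.5 and Table 1 have the battery questionnaires handed out at Visit 4 (1 month after first activation) and Visit 7 (4 months).

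**The concern.** In a two-period crossover, one group logs FAST in period 1 and the other logs it in period 2. A change in battery duration between periods that has nothing to do with strategy therefore enters the FAST minus ACE difference with opposite signs in the two groups. A plain t-test treats this systematic split as random scatter. With equal groups the split cancels in the mean but stays in the standard error. With unequal groups part of it also remains in the mean.

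A shift is plausible here. Subjects are newly activated and the two logs fall three months apart. Under protocol 5.2.6 a log ends when the processor is switched off or when the battery runs out, so recorded duration can depend on daily wear. Protocol 5.1 also concedes, in general terms, that maturation over time is not removed by the crossover.

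At stake are the width and accuracy of the battery-life estimate. That estimate is itself the deliverable, because the first secondary objective is to quantify the benefit.

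**Working it through.** **The plan's own figures.** The documents give no sample size, power, SD or expected difference for battery life. As a check on the method, a paired t-test (noncentral t, one-sided 0.025, 90% power, true difference 0) reproduces the stated co-primary sizes:
- CNC, SD 7.20 rau, margin 10 rau: n = 8 (power 0.918; n = 7 gives 0.862).
- BKB, SD 1.84 dB, margin 2 dB: n = 11 (power 0.900; n = 10 gives 0.863).

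**Inputs for battery life.**
- N = 20, half per sequence (protocol 5.1).
- One-sided 0.025 (SAP 1.4.2.1).
- θ = shift in mean duration, period 2 minus period 1, in units of the within-sequence SD of the FAST minus ACE difference. It is assumed to be the same under either strategy. The documents do not give it, so 0, 0.25, 0.5 and 1.0 are taken.
- True difference for the power figures: 0.765 SD, which gives the plain test 90% power at N = 20 with no shift (assumed).

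**Formulas.** With τ the true difference, n1 subjects FAST first and n2 ACE first:
- Expected difference: τ − θ in Group 1 and τ + θ in Group 2.
- Bias of the plain mean: θ(n2 − n1)/N.
- Inflation of the plain SD: √[1 + 4θ²·n1·n2/(N(N−1))], which at 10/10 is √(1 + θ²·20/19).
- Period-adjusted estimate: the average of the two sequence means, with SE = s_pooled × ½√(1/n1 + 1/n2) on N − 2 degrees of freedom. Its bias is zero for any θ.

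**At 10/10.** The SD inflation is √1 = 1.000, √1.0658 = 1.032, √1.2632 = 1.124 and √2.0526 = 1.433. Simulation (100,000 trials per setting) gives:

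| θ (SD) | Bias, plain | CI width, plain/adjusted | Power, plain v adjusted | Type I error, plain |
|---|---|---|---|---|
| 0 | 0 | 0.997 | 0.900 v 0.899 | 0.025 |
| 0.25 | 0 | 1.03 | 0.888 v 0.899 | 0.022 |
| 0.5 | 0 | 1.12 | 0.849 v 0.898 | 0.015 |
| 1.0 | 0 | 1.43 | 0.662 v 0.898 | 0.003 |

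**At 8/12 (8 FAST first, 12 ACE first).** Bias = θ × 4/20:

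| θ (SD) | Bias, plain | Type I error, plain | Power, plain v adjusted |
|---|---|---|---|
| 0 | 0 | 0.025 | 0.899 v 0.885 |
| 0.25 | 0.05 | 0.036 | 0.924 v 0.887 |
| 0.5 | 0.10 | 0.041 | 0.927 v 0.886 |
| 1.0 | 0.20 | 0.028 | 0.897 v 0.885 |

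The higher plain power in the middle rows comes from the bias and is no advantage. If the imbalance or the shift is reversed, the bias changes sign: at 11/9 with θ = 0.5 it is −0.05 SD, the type I error is 0.008 and power is 0.795 against 0.896. The adjusted test stays near 0.025 throughout.

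**How likely is imbalance?** The supplied text describes no blocking. If randomisation were simple (an assumption), exactly 10/10 would have probability 0.18 and a gap of 4 or more 0.50. SAP 1.2 allows for attrition without giving a rate.

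**The case against.** The strongest reply is that both harms are conditional. A reader might infer that the t-test does lose precision and is biased. The documents do not support that, because they neither state nor quantify a period effect on battery life. With θ = 0 the plain test is unbiased and as good as the adjusted one or slightly better. At the planned 10/10 there is no bias for any θ.

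A reader might also take the refitting schedule as evidence of drift: "fine-tuning of the cochlear implant stimulation levels (i.e. MAP) will occur at 1 week and 1 month after receiving each strategy". That schedule is the same in both periods, and both questionnaires are handed out at the 1-month visit on the strategy in use. It does not show that stimulation levels differ between the two logs. A shift over time since first activation, including through changing wear, remains possible but is not documented.

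Marked imbalance may also be rare. If the trial starts at 10/10 and three subjects drop out for reasons unrelated to group, all three come from one group with probability 2·C(10,3)/C(20,3) = 240/1140 = 0.21. Otherwise the split is 9 and 8, and the bias is only θ/17 ≈ 0.06θ. On the other side, protocol 9.2 warns that converting between strategies can be hard, so dropout could differ by sequence.

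Nor does the omission systematically favour FAST. At 10/10 the test is conservative, and under imbalance the sign of the bias depends on which group is larger and which way duration shifts.

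Finally, a reader might infer that subjects with only one completed questionnaire are lost. A paired difference does need both values, but SAP 1.4.2.1 does not say how incomplete logs are handled, and the gain from keeping such subjects has not been quantified. The point does not rest on this.

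These replies reduce the weight of the point. They give no reason to leave period out of the analysis of a randomised crossover.

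**Conclusion.** The point stands in conditional form. The battery-life analysis omits period, while the co-primary analyses of the same subjects and sequences include it. If battery duration shifts between periods, the reported interval is wider than it need be: by about 3%, 12% and 43% at 10/10 for shifts of 0.25, 0.5 and 1.0 SD, and not at all for no shift. With unequal groups the estimate is also biased, by 0.05, 0.10 and 0.20 SD at 8/12. The shifts and the 8/12 split are assumptions. The calculation also takes the shift to be equal under both strategies. The documents do not show that a shift exists. This is a minor improvement to a secondary endpoint, and the definition of study success, which rests on the two co-primary endpoints, is not touched.

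**What to change.** In SAP 1.4.2.1, replace the t-test with the mixed model already specified for the co-primary endpoints: treatment, period and sequence as fixed effects and a random subject effect, fitted to each subject's mean battery duration in each period. Test FAST − ACE > 0 one-sided at 0.025 and report the model-based 95% confidence interval. Make the change before the battery data are seen, so that the choice to adjust is not post hoc.

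The cost is one sentence and one degree of freedom (18 instead of 19 with 20 complete subjects). If there is no period effect, the power loss is negligible at 10/10 (0.899 against 0.900) and small at 8/12 (0.885 against 0.899). In return, the estimate is unbiased and the test keeps its nominal level whatever the common shift between periods.
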